#### 8.5.2.2. Incidence rates of hospitalization due to CAP for incident users

Table 4 Incidence rate of hospitalizations due to CAP (Trelegy 100 group)

Total Patient Years	Number of patients with hospitalizations due to CAP	Incidence rate (/1000 Patient Years)	
		Estimate	95% confidence interval
3225* 	258	80	[70.54, 90.38]
	323	100	[89.53, 111.70]
	387	120	[108.34, 132.57]
	452	140	[127.53, 153.69]
1935* 	155	80	[67.99, 93.75]
	194	100	[86.65, 115.40]

	232	120	[104.96, 136.36]
	271	140	[123.87, 157.76]

\* 1: 50% of the sales forecast

\* 2: 30% of the sales forecast

Note: Exact poisson confidence intervals using chi-square distribution

Table 5 Incidence rate of hospitalizations due to CAP (MITT group)

Total Patient Years	Number of patients with hospitalizations due to CAP	Incidence rate (/1000 Patient Years)	
		Estimate	95% confidence interval
2185 *1	175	80	[68.66, 92.88]
	219	100	[87.39, 114.42]
	262	120	[105.83, 135.34]
	306	140	[124.79, 156.65]
1311 *2	105	80	[65.51, 96.96]
	131	100	[83.55, 118.57]
	157	120	[101.76, 140.02]
	184	140	[120.80, 162.16]

\* 1: 50% of the sales forecast

\* 2: 30% of the sales forecast

Note: Exact poisson confidence intervals using chi-square distribution

## 8.6. Data Management

This study is performed using health insurance claims (outpatient and inpatient) data provided by MDV (Tokyo, Japan). The data extraction conditions will be described in the statistical analysis plan.

### 8.6.1. Data handling conventions

Details of data handling will be described in the statistical analysis plan.

### 8.6.2. Resourcing needs

The analysis for this study will be outsourced to CMIC Co., Ltd. (contract research organization (CRO)). After being independently analysed by double programming within CRO, the results will be delivered to GSK. The GSK analyst then checks if the analyses are done correctly. This study is overseen by a senior PhD level Epidemiologist and department manager of post-marketing surveillance Dept. at GSK.

### 8.6.3. Timings of assessment during follow-up

For timings of assessment, refer to “Sec 5 MILESTONES”.

## 8.7. Data Analysis

An overview of the analytical methods is provided in this protocol. Details of the analysis methods are provided in the statistical analysis plan.

Data of this study are provided by MDV. GSK transfers the data received from MDV to CRO and statistical analysis is conducted by the person responsible for performing the statistical analysis of CRO.

### 8.7.1. General considerations

If there are more than 10% of missing data within covariates, we will discuss at the timing of the Data review (refer to “Sec 5 MILESTONES”) whether to supplement the missing data or exclude them from covariates. The result of the discussion will be approved by the senior manager. The confidence coefficient for the interval estimation is set at 95%. SAS version 9.1 (SAS Institute, Cary, North Carolina) or later is used as statistical analysis software.

### 8.7.2. Study population

The number of patients who meet or don't meet eligibility criteria (refer to “Sec 8.2 Study

Population and Setting”) is shown in flow chart.

### 8.7.3. Endpoints

Endpoint will be occurrence of pneumonia including those with COVID-19 code.

We will include patients with COVID-19 in the main analysis to increase generalizability of the results. Occurrence of pneumonia excluding those with COVID-19 code will be estimated separately as a supplemental analysis.

- Scientific knowledge has not been accumulated to explain how COVID-19 affects pneumonia occurrence.
- Inflated occurrence of pneumonia during COVID-19 pandemic period cannot be interpreted scientifically (including interaction between COVID-19 infection, ICS exposure and pneumonia events)

The above approach is applicable to primary endpoints (8.7.3.1) and secondary endpoint-a) (8.7.3.2.1).

#### 8.7.3.1. Primary endpoints

##### 8.7.3.1.1. HRs for hospitalization due to CAP among incident Trelegy 100 users compared to incident MITT users

To adjust covariates (refer to “8.3.3.1 Covariates”), propensity score which is defined as a probability of Trelegy 100 treatment selection conditional on observed covariates will be estimated for an individual using logistic regression. Multicollinearity will be considered when selecting covariates. By inverse probability of treatment weighted Cox models using the propensity score, the marginal HR along with 95% confidence intervals will be estimated among incident Trelegy 100 users compared to incident MITT users. Variance estimation will be calculated using robust sandwich variance method.

#### 8.7.3.2. Secondary endpoints

##### 8.7.3.2.1. Incidence rate of hospitalization due to CAP

Incidence rates and 95% confidence interval of outcomes (refer to “Sec 8.3.2 Outcome definitions”) for overall or incident users in Trelegy 100 group or MITT group will be estimated by using Poisson regression model. Incidence rates of outcomes sorted by diagnostic imaging conducted (X-ray only, CT scan only, or X-ray combined with CT scan) will be estimated as well. Also, The unadjusted and adjusted rates by covariates (refer to “8.3.3.1 Covariates”) along with 95% confidence intervals will be calculated for each group for overall or incident users. Multicollinearity will be considered when selecting covariates.

##### 8.7.3.2.2. Characteristics of users of Trelegy 100 or MITT among COPD patients

The distribution of patient information (refer to “Sec 8.3.3.1 Covariates” and “8.3.3.2 Other variables”) is summarized for overall or incident users in Trelegy 100 group or MITT group. For the categorical data, the number and proportion of patients will be calculated. For the continuous data, descriptive statistics values will be calculated. Regarding the test for differences between groups of patient information,  $\chi^2$  test or analysis of variance (ANOVA) will be performed.

##### 8.7.3.2.3. Characteristics of the Unweighted and Weighted incident Trelegy 100 users vs incident MITT users

To adjust covariates (refer to “8.3.3.1 Covariates”), propensity score will be estimated for an individual using logistic regression. Multicollinearity will be considered when selecting covariates. By inverse probability of treatment weighting using the propensity score, the descriptive statistics and standardized differences will be estimated. Patient characteristics will be evaluated during look-back period and will be compared between unweighted and weighted incident Trelegy 100 users and incident MITT users. Descriptive statistics will include mean and standard deviation (SD) values for the continuous variables, and relative proportions for the

categorical variables. Differences in patient characteristics between unweighted and weighted users will be assessed using standardized differences. A standardized difference of less than 10% is considered not statistically relevant.

#### **8.7.3.2.4. Graph of cumulative incidence of first occurrence of hospitalization due to CAP Curves**

The date of outcome onset will be defined as the event date, and the probability of the event in the Trelegy 100 group or MITT group will be illustrated using non-parametric cumulative incidence function for overall or incident users. Death will be considered as the competing event. In addition, cumulative incidence of hospitalization due to CAP is also plotted using inverse probability of treatment weighting in incident users only.

#### **8.7.3.2.5. HRs for hospitalization due to CAP between subgroups within Trelegy 100 or MITT group**

The univariate and multivariate HRs divided by patient information (refer to “8.3.3.1 Covariates”) along with 95% confidence intervals will be calculated for each group for overall or incident users. Also, forest plots will be created. In addition, multicollinearity will be considered when selecting variables for multivariate analysis. HRs will be calculated using cause-specific hazard model in the competing event setting. Death will be considered as the competing event.

#### **8.7.3.2.6. Change over time in the proportion of triple therapy among COPD patients**

The status of COPD maintenance therapy for COPD patients will be counted for each year, and the proportion of COPD maintenance therapy based on the number of COPD patients will be calculated. In addition, the details of triple therapy will be calculated. The change over time in the proportion of any ICS-containing therapies and comorbid asthma among COPD patients will be calculated. Over-time refers to 360 days prior to date of launch of Trelegy 100, and 0-359 days, 360-719 days, 720- 1079 days after the launch. Target population for this objective includes COPD patients regardless of treatment.

#### **8.7.3.2.7. Change over time in the proportion of COVID-19 among follow-up period**

The number of patients with COVID-19 in each group among the follow-up period will be counted for each month, and the proportion of patients with COVID-19 based on the number of each group will be calculated. Also, the graph will be created. Over-time refers to calendar month after launch of Trelegy 100. Target population for this objective includes COPD patients regardless of treatment. In case there is a surge in COVID-19 cases in Japan during the study period, we will consult with PMDA to add a supplemental analysis by time period to see the impact of COVID-19 pandemic on the results.

#### **8.7.3.3. Sensitivity analysis**

The primary endpoints and explanatory analysis will be performed by the following conditions. When one of the 3 conditions are applied, other 2 conditions will not be applied but original conditions will be kept.

- One of inclusion criteria is changed from “patients with ICD-10 codes for COPD (J42, J43 or J44)” to “patients with ICD-10 codes for COPD (J42, J43 or J44) and with prescription of any inhaled medicine with the indication of COPD”, at the index date and on at least 2 visits (outpatient visit or hospital admission) in the look-back period
- Overlap of 3 components for MITT group is changed from at least 1 day to at least 14 days (including the index date)
- Follow-up period is changed from maximum 360 days to maximum 1,440 days (after the index date)

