**Figure1 Study design**

Identification of the study population will be conducted using health insurance claims data (outpatient and inpatient) and Diagnosis Procedure Combination (DPC) data. Patients surveyed are aged 40 years or older at the start date of prescription (index date) for Trelegy 100 or MITT during the 1,080-day identification period (from May 22, 2019 to May 5, 2022).

In this protocol, one month is defined as 30 days based on the manner of Post-marketing Surveillance in Japan.

In this study, data will be collected retrospectively with the 1,080-day identification period to have as much patient data as possible within the time frame to submit study results for the reexamination application for Trelegy 100. We plan to conduct data review in 2022 as described at the bottom of ABSTRACT, and we need time to agree on the protocol with PMDA after the endorsement by Protocol Review Committee (PRC), and thus we prepared this protocol in 2020.

Patients with records of International Statistical Classification of Diseases and Related Health Problems, Tenth Revision (ICD -10) codes for COPD (J42, J43 or J44), one record at the index date and additional 2 records (outpatient visit or hospital admission) in the 360 days look-back period [index date, index date -360 days]. This criterion is to exclude patients with infrequent visits and to secure collection of patient characteristics data in the look-back period.

At least one record (outpatient visit or hospital admission) with any ICD-10 codes in the 180 days

prior to the start date of look-back period [index date – 360 days, index date – 540 days]. This criterion is to secure patient records throughout the look-back period.

Follow-up period will be from the index date (including the index date) to the earliest date of the followings: 1) admission date of hospitalization due to CAP or 2) date of death or 3) end date of exposure period with Trelegy 100 or MITT by discontinuation (defined in 8.3.1.1. continuation of exposure), or 4) 360 days after the index date.

In base case analysis, the 360-day follow-up period will be applied, while the 1,440-day follow-up period will be used in sensitivity analysis.

The reason for the 360-day follow-up period is based on the article by Suissa et al. which demonstrated that the effect of ICS on pneumonia occurrence among COPD patients peaked in the first year of use.

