## 8.3. Variables

### 8.3.1. Exposure definitions

There are two types of triple therapy: single inhaler triple therapy (SITT) (Trelegly 100, other than Trelegly 100) and MITT as described below. Exposures of this study are Trelegly 100 and MITT.

1. Single inhaler triple therapy (SITT):
  - a. Trelegly 100 (FF/UMEC/VI delivered in an Ellipta inhaler)
  - b. SITTs other than Trelegly 100 (for secondary objective-d) only
2. Multiple inhaler triple therapy (MITT):
  - a. LAMA combined with fixed dose ICS/LABA (two devices), or
  - b. LAMA/LABA with ICS (two devices), or
  - c. Fixed dose ICS, LABA, and LAMA (three devices)
  - d. Any other combinations of the 3 components (ICS, LAMA and LABA)

The date of the first prescription of Trelegly 100 or MITT between May 22, 2019 and May 5, 2022 will be identified as the index date.

Only SITT users of Trelegly 100 Ellipta with COPD indication will be eligible in this study.

MITT user will be defined as overlapping prescriptions of LAMA, ICS, and LABA, in either two or three devices. Inhaled respiratory medicines have different indications e.g. COPD only, asthma only, or both COPD and asthma. Among medicines composing MITT, at least one medicine must have an indication of COPD at the timing of prescription by considering that the indication of a medicine may

change during the study period. The initial inhaler triple therapy initiation during the identification period that will be used to mark the index date will be defined as the date when the 3rd component is added to the treatment regimen (or 2nd/3rd component if a dual therapy [e.g. ICS/LABA or LAMA/LABA] is added to a monotherapy).

After identifying MITT use by the above rules, continuation of the MITT use will be determined by the rules for exposure continuation described in Sec 8.3.1.1.

All patients who have at least one day of overlap of all 3 components will be classified as MITT users as a base case analysis. The definition of MITT exposure including only one day of overlap of ICS, LABA and LAMA on the index date may overestimate the MITT exposure, and thus another option to include patients who have at least 14 days (index date plus 13 days) of overlap of all 3 components will be given as a sensitivity analysis.

Trelegy 100 or MITT prescriptions in the database will be defined using Anatomical Therapeutic Chemical (ATC) codes (atccode) and Health claim code (receiptcode).

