### 8.3.2. Outcome definitions

#### 1. Algorithm of outcome definitions

- Hospitalization due to CAP which occurs 1 day or more after the index date. Admission date will be treated as the first day of hospitalization due to CAP.

Hospitalization due to CAP during follow-up period (defined in 8.1 Study Design) will be identified using DPC data. ICD-10 codes, DPC disease segments, prescription data and diagnostic imaging data will be used as follows.

#### Definition 1

- 1) Any of the ICD-10 codes of J10.0, J11.0 or J12-J18
- 2) The above ICD-10 codes in DPC disease segment #21 (disease which triggered the hospitalization)
- 3) Prescription of antibiotics (ATC code: J01) on the day of admission or the next day of hospitalization
- 4) Diagnostic imaging (X-ray or computerized tomography (CT) scan) conducted between 2 days before and 7 days after the hospitalization

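### In the 14-day-overlap sensitivity analysis, some MITT patients qualify only through a refill after the index date, yet follow-up starts at the index date, so this HR can be biased slightly upward

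*Protocol*

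**What the plan says.** Protocol 8.3.1 classifies a patient as a MITT user from one day of overlap of the three components. It concedes that this may overstate MITT exposure and offers "another option to include patients who have at least 14 days (index date plus 13 days) of overlap of all 3 components" as a sensitivity analysis. Section 8.7.3.3 repeats the change for the MITT group only: "Overlap of 3 components for MITT group is changed from at least 1 day to at least 14 days (including the index date"). It adds that when one sensitivity condition is applied, "other 2 conditions will not be applied but original conditions will be kept".

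The rules that stay in force are these:

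- Start of follow-up (8.1, under Figure 1): "Follow-up period will be from the index date (including the index date) to the earliest date of the followings", with a cap of 360 days.
- Outcome (8.3.2): "Hospitalization due to CAP which occurs 1 day or more after the index date".
- MITT index date (8.3.1): the day on which the last "component is added to the treatment regimen".
- How overlap is measured (8.3.1): "MITT user will be defined as overlapping prescriptions of LAMA, ICS, and LABA, in either two or three devices". Section 8.3.1.1 estimates each prescription's length from the package insert and takes 30 days as standard.

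No section moves the start of follow-up for this analysis, sets a matching condition for Trelegy 100, or says whether prescriptions issued after the index date count towards the 14 days.

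**The concern.** Days 1 to 13 serve two purposes in the MITT group. They are the window in which a patient may still have to qualify, and they are time at risk in which events count. Because the MITT index date is the day the last component is added, an earlier component may be part-used by then. A patient with fewer than 14 days of it left enters the analysis only if it is refilled after index. To be refilled as an outpatient, that patient must first stay alive and out of hospital. Those who do not can be removed along with their event, while those who do keep their person-time from the index date.

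Trelegy 100 delivers all three components in one prescription and is subject to no overlap rule, so all its early events count. The loss is one-sided and pushes the Trelegy/MITT HR up.

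Of the three sensitivity analyses in 8.7.3.3, this is the only one that addresses the overstatement of MITT exposure conceded in 8.3.1. If it carries a bias of its own, a shift from the base case cannot be credited cleanly to the stricter exposure definition.

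**Working it through.** **Inputs from the protocol.** Incident users: 1935 to 3225 on Trelegy 100 and 1311 to 2185 on MITT (8.5). CAP rate: 80 to 140 per 1000 patient-years (8.5). Follow-up cap: 360 days (8.1). Standard prescription: 30 days, grace period: 30 days (8.3.1.1).

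**Assumptions, not in the documents.** f is the share of MITT patients who need a refill on days 1 to 13 (range 0 to 100%). d is the number of immortal days per such patient: 13 at most, and (1 + 13)/2 = 7 on average if the day of need is uniform over days 1 to 13. T is mean follow-up: 330 down to 120 days as a working range, with 360 (the cap) and 60 (one 30-day prescription plus grace) as extremes. The hazard is constant.

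**The plan's own figure first.** Table 1 in 8.5.1 gives a 6.0% probability of observing HR > 3 with 3225 and 2185 users, an 8% annual rate and a true HR of 2.5. Total events = 5410 × 0.08 = 432.8, split in the ratio 3225 × 2.5 : 2185, giving 340.5 and 92.3. SE = √(1/340.5 + 1/92.3) = 0.117. P = Φ[(ln 2.5 − ln 3)/0.117] = Φ(−1.55) = 6.0%. All 40 cells of Table 1 reproduce in this way.

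**Events within reach of the rule.** Expected MITT events on days 1 to 13 are n × rate × 13/360. The lowest value is 1311 × 0.08 × 13/360 = 3.8 and the highest is 2185 × 0.14 × 13/360 = 11.0. No more than these could be selected out. With f = 50% and d = 7, the corresponding figures are 1311 × 0.08 × 0.5 × 7/360 = 1.0 and 2185 × 0.14 × 0.5 × 7/360 = 3.0.

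**Effect on the HR.** If the events in the immortal days are removed and the person-time is kept, the MITT rate falls by the factor 1 − f·d/T, so the HR is multiplied by 1/(1 − f·d/T).

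| f | d | T = 360 | T = 330 | T = 120 | T = 60 |
|---|---|---|---|---|---|
| 0 | any | 1.000 | 1.000 | 1.000 | 1.000 |
| 25% | 7 | 1.005 | 1.005 | 1.015 | 1.030 |
| 50% | 7 | 1.010 | 1.011 | 1.030 | 1.062 |
| 100% | 7 | 1.020 | 1.022 | 1.062 | 1.132 |
| 100% | 13 | 1.037 | 1.041 | 1.121 | 1.277 |

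For example, 1/(1 − 0.5 × 7/330) = 1.011 and 1/(1 − 0.5 × 7/120) = 1.030. A simulation of the refill mechanism (12% per 360 days, day of refill uniform over days 1 to 13, f = 50%) gave 1.010 at 360 days and 1.062 at 60 days, in agreement with the formula.

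**Scale against the HR > 3 criterion.** With the 360-day upper bound of 1.037, the 6.0% above becomes 10.7%. The matching cell for 1935 and 1311 users moves from 11.4% to 16.8%. At a true HR of 2 and the 8% rate, the probability stays at or below 0.5% for both sample sizes. Table 1 describes the primary analysis, so these figures only show scale; the primary HR itself does not move.

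**The case against.** A reader might infer that the rule gives immortal time to the MITT group as a whole. The documents do not support that. Overlap is calculated from prescription periods of estimated length, not from observed use. A patient who holds at least 14 days of every component at index therefore qualifies that day and stays in even if admitted on day 5. With 30 days as the standard prescription, this may be the common case, and the earlier component may well be renewed at the same visit.

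Three further points reduce the size. First, a refill-dependent patient is exposed to selection only until the refill, so charging all 13 days is a ceiling. Second, an early admission need not lead to exclusion: the database holds inpatient prescriptions (8.4), and a component prescribed during the stay could complete the overlap. Third, a larger effect could be obtained by supposing a raised hazard in the first two weeks, but 8.1 says only that the effect of ICS on pneumonia peaks in the first year.

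It can also be said that the base case is safe, since one day of overlap is met on the index date, and that an upward bias cannot give false reassurance about HR > 3. Both points stand.

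The argument that the detail belongs to the SAP is weaker. Section 8.3.1.1 leaves the estimation of prescription length to the SAP, but the qualifying window, the start of follow-up and the instruction to keep the other conditions are all fixed in the protocol. What remains is a one-sided rule that, as written, allows qualification after follow-up has begun.

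**Conclusion.** The flaw is real but narrow. It affects only those MITT patients who need a refill on days 1 to 13, in one sensitivity analysis, and it runs upward, against Trelegy 100. At a 50% refill share, 7 immortal days on average, a constant hazard and mean follow-up of 330 down to 120 days, the HR rises by about 1% to 3%, or roughly one to three MITT events at the planned sizes and rates with full 360-day follow-up. The upper bound (100% share, 13 days) is about 4% at 330 days and 12% at 120 days. If no patient needs a refill, the bias is zero. The refill share and mean follow-up are assumptions, so none of these figures is a forecast.

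It would go too far to conclude that the primary HR is compromised or that the MITT group is immortal throughout. The supported conclusion is that the plan's one check on overstated MITT exposure should not carry an avoidable bias of its own.

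**What to change.** State in 8.3.1 and 8.7.3.3 that the 14-day overlap is determined only from prescriptions issued on or before the index date. Eligibility is then settled at the start of follow-up and the HR factor from this source is 1.00. The cost is one sentence in each place, and some MITT patients who would have completed the overlap by refill leave this sensitivity analysis.

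An alternative is a common landmark: start follow-up on day 14 in both groups, among patients alive, CAP-free and still under follow-up. This also removes the bias, but it loses early events and up to 14/360, about 4%, of the maximum person-time in both groups. It also changes more than one feature relative to the base case, which fits less well with the one-condition-at-a-time design of 8.7.3.3. The first option is the simpler.
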